13.0 STATISTICAL CONSIDERATIONS

13.1 Phase I Study Endpoints

13.1.1 Primary Endpoint

The primary endpoint of the phase I portion is to either reach the maximum tolerated dose (MTD) or a dose of 50 Gy total (whichever comes first) by escalating the dose of SBRT toward the tumocidal dose of 50 Gy total. Patients will be treated in cohorts of seven to fifteen,.. Toxicity will be graded using the NCI Common Toxicity Criteria for Adverse Events (CTCAE) v. 3.0. A dose- limiting toxicity (DLT) is any treatment-related grade 3, 4, or 5 toxicity in the following categories (specific conditions listed in section 6.9): gastrointestinal, renal, genito-urinary, sexual- reproductive, or neurological. A DLT will also include any treatment-related grade 4 or 5 toxicity related in the following categories (specific conditions listed in section 6.9): constitutional symptoms. In addition, any other grade 4 or 5 toxicity attributed to the therapy constitutes DLT. All reported DLTs will be verified by study chair, data monitoring committee, and independent review before final determination that a DLT has in fact occurred. Doses will be escalated an additional 0.5 Gy per treatment for 5 treatments (total 2.5 Gy per increment). The phase I portion of the study will be completed when either of the following events occur: 1) the MTD for a cohort is reached or 2) when the highest protocol dose level is treated and tolerated (10 Gy per fraction, total 50 Gy) where we consider the therapy likely to be tumocidal per determination of the investigators.

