13.1.2 Phase I Dose Escalation

The phase I study is designed to end if the rate of DLTs within 90 days from the start of treatment is 33% or higher. For each dose level cohorts, a total of seven to fifteen patients will be enrolled. If zero out of the first seven with 90 day follow-up, two or fewer out of the first nine with 90 day follow-up, three or fewer out of the first twelve with 90 day follow-up, or four or fewer out of the first fifteen of patients with 90 day follow-up experience a DLT as defined above, then the dose will escalate to the next dose level. If three or more of the first nine patients, four or more of the first twelve, or five or more of the first fifteen patients experience a DLT, then the MTD will be considered to have been exceeded. The MTD will be defined as the immediately previous lower dose level tolerated. The probability that at least two of nine patients will experience a DLT when the true rate of acute DLTs is 33% is 0.80; that is, the probability of making the correct decision if the true DLT rate is at least 33% is 0.80.

The sample size of the phase I component of this study will not exceed 45 patients.

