13.3 Sample Size

13.3.1 Overview: The primary goal of this study is to estimate the rate of late grade 3-5 genitourinary and gastrointestinal toxicity following treatment with stereotactic body radiation therapy. For purposes of this phase II study, late toxicity will be defined as toxicity occurring 270-540 days (i.e., 9-18 months) from the start of radiotherapy. It is graded based on CTCAE v 3.0.

13.3.2 Sample Size Derivation: The phase II component of this study is designed to test whether late GU/GI toxicity at 270-540 days from the start of treatment following the protocol treatment is above 10%. The sample size is determined so that the probability of rejecting the treatment because of excessive late toxicity is 90% if the true late toxicity rate is 23% or higher. Assuming an exponential distribution for time from the end of the acute period (*270 days from the start of protocol treatment*) to the occurrence of late toxicity, the hazard rate for the expected 10% toxicity rate and the unacceptable 23% toxicity rate is 0.006/month and 0.015/month, respectively. Following the asymptotic property of the observed hazard and using Z-test for the logarithm of the hazard ratio [35-36], we require 12 cases with severe late GU/GI toxicity. Thus, 47 patients are required to be accrued within three to four years and be followed for 270 days after the acute period (i.e., a total of 540 days) to have a statistical power of 90% with a one-sided significance level of 0.05. Considering 5% ineligible cases and lack-of-data cases, the sample size of the phase II component of this study is 50 patients. Patients treated in phase I at the dose level ultimately used in phase II will be included in the phase II analysis as part of the 50 patient trial.

The sample size of the phase II component of this study will not exceed 50 patients.

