14.2 Early Stopping for Toxicity

In phase I, stopping for toxicity will be related to dose limiting toxicity as described in the statistical section. Early stopping of the phase II portion of this protocol will be based on unacceptable toxicity, defined as grade 3 - 5 toxicity related to the following organ systems: gastrointestinal, renal, genitor-urinary, sexual, reproductive, neurological, blood, bone marrow, or constitutional symptoms OR any other grade 4 or 5 toxicity attributed to the therapy occurring in 30% or more of treated patients. If a single patient has more than one unacceptable toxicity, they will only be counted as one unacceptable toxicity for this analysis.

Three interim analyses of toxicity are planned after 25% (12 patients), 50% (24 patients), and 75% (36 patients) of the total number of evaluable patients to be accrued in phase II. These interim analyses will be done after patients have finished their toxicity assessment periods for each group (i.e., 90 days of post therapy follow-up).

The following early stopping rules reject the null hypothesis that the toxicity rate is less than or equal to 10% in favor of the alternative hypothesis that the toxicity rate is at least 30% with an overall Type I error rate of no more than 0.05⁵:

- 6 or more cases of unacceptable toxicities out of the first 12 evaluable patients, or
- 7 or more cases of unacceptable toxicities out of the first 24 evaluable patients, or
- 8 or more cases of unacceptable toxicities out of the first 36 evaluable patients.

The final analysis will test the same null hypothesis using the rejection rule of 10 or more patients with unacceptable toxicities out of the total sample of 47 evaluable patients. This will insure an overall significance level of 0.05 for the final conclusion. If more than 47 of the 50 accrued patients are evaluable, then the first 47 evaluable patients will be used for this analysis.

If the number of unacceptable toxicities observed demonstrate via the monitoring rules above that the treatment-related unacceptable toxicity rate is 30% or more, consideration

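### Phase I patients selected for few DLTs count among the 50 phase II patients: if they come first, the 6-of-12 look cannot trigger on 90-day DLTs alone, and the pooled 90-day toxicity rate is biased down

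*Combined protocol and SAP*

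**What the plan says.** Section 13.3.2 places the carried-over patients inside the phase II sample of 50: "Patients treated in phase I at the dose level ultimately used in phase II will be included in the phase II analysis".

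Those patients have passed a toxicity screen. Under 13.1.1, phase I ends at the MTD or "when the highest protocol dose level is treated and tolerated". Section 13.1.2 sets the pass rule: "If zero out of the first seven with 90 day follow-up, two or fewer out of the first nine with 90 day follow-up", then three or fewer of 12, or four or fewer of 15. The fail rule is "If three or more of the first nine patients, four or more of the first twelve, or five or more of the first fifteen". If a level fails, phase II uses the lower level that was tolerated, so the phase II dose has passed in either case. The screen is on the "rate of DLTs within 90 days from the start of treatment is 33% or higher".

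Section 14.2 sets four boundaries for unacceptable toxicity: "6 or more cases of unacceptable toxicities out of the first 12 evaluable patients", then 7 of 24, 8 of 36, and 10 of 47 at the final analysis. It tests 10% against 30% and states an overall type I error of no more than 0.05. It gives no power. It describes the patients as those to be accrued in phase II, yet takes the 47 from the 50 accrued. It does not say whether carried-over patients are among the first 12, and it makes no allowance for their selection.

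**The concern.** The boundaries in 14.2 are binomial and treat the patients as an unselected sequence. If the sequence opens with patients who are there because few of them had a DLT, the early counts are capped. The first safety look may then be unable to respond to the events it is most likely to be watching. The pooled 90-day toxicity rate would also combine a selected group with an unselected one and come out too low. Both effects run towards making the dose look safer, and a reader of the final report could not see their size from pooled figures alone.

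**Working it through.** **Inputs.** Phase I rules from 13.1.2; boundaries 6/12, 7/24, 8/36 and 10/47 and rates 10% and 30% from 14.2; carry-over from 13.3.2. Two assumptions are not in the documents: carried-over patients come first, and DLT and unacceptable toxicity are the same event with a constant risk *p* per patient.

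**1. The plan's own figure.** The method is an exact binomial recursion, patient by patient, removing the probability that crosses a boundary at each look. With unselected patients:
- *p* = 10%: 0.0005 + 0.0071 + 0.0176 + 0.0054 = 0.031. The stated bound of 0.05 is reproduced.
- *p* = 30%: 0.1178 + 0.4947 + 0.2777 + 0.0559 = 0.946.

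**2. Largest DLT count among the first 12.** Carried-over maximum plus every new patient up to number 12:
- 0 of 7, plus 5 new: 5
- 2 of 9, plus 3 new: 5
- 3 of 12: 3
- 4 of 15: at most 4

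None reaches 6.

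**3. Operating characteristics given a phase I pass.** The recursion now starts from the phase I count, conditional on passing. Path A: decided at 7 or 9 patients. Path B: 15 patients treated, with the limits at 9, 12 and 15 all met.

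| | Unselected | Path A | Path B |
|---|---|---|---|
| Crosses at look 1, true 30% | 0.118 | 0 | 0 |
| Crosses by patient 24, true 30% | 0.1178 + 0.4947 = 0.61 | 0.38 | 0.28 |
| Overall rejection, true 30% | 0.946 | 0.900 | 0.876 |
| Overall rejection, true 10% | 0.031 | 0.022 | 0.019 |
| Expected pooled 90-day rate, true 30% | 30% | 27.4% | 26.4% |
| Expected pooled 90-day rate, true 10% | 10% | 9.7% | 9.7% |

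Check of 27.4%: on path A at a true 30%, a passing cohort has on average 8.64 patients and an observed rate of 16%. So (8.64 × 0.16 + 38.36 × 0.30) / 47 = (1.38 + 11.51) / 47 = 0.274.

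**4. Whole-trial detection at a true 30%.** P(phase I fails) + P(passes) × P(14.2 rejects, given a pass):
- Path A: 0.537 + 0.463 × 0.900 = 0.954
- Path B: 0.636 + 0.364 × 0.876 = 0.955

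Both slightly exceed the 0.946 of the 14.2 rule alone.

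**5. Late primary rate (270–540 days).** Suppose a patient with a DLT has *k* times the late risk of one without; *k* is an assumption. Take a DLT rate of 30%, a true late rate of 23%, path A, and an expected pooled DLT share of 0.274. The late risk without a DLT is 0.23 / (0.7 + 0.3*k*).
- *k* = 1: expected estimate 23.0%, no bias.
- *k* = 3: risks 0.144 and 0.431; 0.274 × 0.431 + 0.726 × 0.144 = 22.3%.
- *k* = 5: risks 0.105 and 0.523; 0.274 × 0.523 + 0.726 × 0.105 = 21.9%.

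**The case against.** The strongest reply is that the first look is silent because a stricter rule has already been applied to the same patients. Phase I rejects at 3 of 9. At a true 30% that has probability 0.537, against 0.118 for 6 of 12. Setting 0.118 beside 0 conditions on a pass and leaves out the doses already rejected. This stands: step 4 shows no loss of detection over the whole trial. Section 14.2 also calls for review if the rate exceeds 30% at any time in five years of follow-up.

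Three stronger readings may suggest themselves; the documents do not support them.

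- *The error statement in 14.2 is wrong.* It is not. The only error rate given there is the type I bound, and selection lowers that error from 0.031 to about 0.02.
- *The first look can never trigger.* That needs the carried-over patients to come first, which 14.2 does not say, although taking the 47 from the same 50 points that way. It also needs DLT and unacceptable toxicity to coincide, which they do not. A DLT is "any treatment-related grade 3, 4, or 5 toxicity in the following categories" listed in 13.1.1, but for constitutional symptoms only grade 4 or 5 counts. Section 14.2 adds grade 3 constitutional and grade 3 blood or bone marrow events, and follows patients to 90 days after therapy rather than from its start. Such events could bring the count to 6.
- *The primary late toxicity rate is biased down.* Phase I does not select on events at 270–540 days, and 13.2.1 counts an earlier event only if it persists at grade 3–5 after day 270. Persistence is a possible link, but its strength is unknown.

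Pooling patients treated at the same dose is in itself an acceptable choice.

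**Conclusion.** The point holds, within limits. The plan carries patients selected for few DLTs into phase II, does not say whether they count in the looks, and makes no allowance if they do. If they come first, 90-day DLTs alone cannot trigger the first look. At a true 30%, the chance of crossing by patient 24 falls by about 23 to 34 percentage points, overall rejection by about 5 to 7 points, and the expected pooled 90-day rate by about 2.6 to 3.6 points. At a true 10% the bias is about 0.3 points.

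These figures rest on the assumed ordering and on treating the two toxicity definitions as one. What is affected is the first look, the timing of the second, and the pooled 90-day estimate. The stated type I bound and whole-trial detection are not harmed. For the late primary rate the bias is zero without an early–late link and about 1 point under the assumed ratios of 3 to 5; its real size is unknown. A change is worth making because it is cheap.

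**What to change.** 1. Keep pooling. Pre-specify the late and unacceptable toxicity rates in newly enrolled phase II patients only, beside the pooled rates. That set has 50 − 15 = 35 to 50 − 7 = 43 patients. Cost: one extra table, with wider confidence limits than the pooled estimate.
2. State in 14.2 whether carried-over patients count in the looks.
   - If they do, recompute the boundaries and operating characteristics conditional on the phase I pass, and report both.
   - If they do not, base every look on newly accrued patients and restate the look sizes and the final 47, since only 35 to 43 of the 50 are then new.

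   Cost: a sentence and one recalculation.

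Do not move only the first look to 12 new patients. After 7 to 15 carried-over patients, those 12 end at overall patient 19 to 27, which crowds or overtakes the pooled look at 24.

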13.4 Patient Accrual and Study Duration

13.4.1 It is expected that it will take approximately three to five years to complete the study. The analysis for late toxicity will be carried out after each patient has had at least 270 days (i.e., 9 months) of follow-up from the end of the acute period, a total of 540 days (i.e., 18 months) of follow-up. For the secondary endpoint of biochemical failure, an additional 18 months of follow-up are needed to estimate the 3-year failure rate. Study-related data will be stored for 5 years after termination of the study when accrual is no longer taking place and all patients have discontinued follow-up procedures. Blood drawn for translation research will be kept indefinitely or until exhausted.

13.5 Analysis Plan

Interim Reports: Interim reports will be prepared every six months until the results of the study are published. In general, the interim reports will contain information about patient accrual rate with projected completion dates of the trial, status of QA review and compliance rate of treatment per protocol, and the frequencies and severity of toxicity.

13.5.2 *The Analysis of Severe Late GU/GI Toxicity:* This analysis will be carried out when each patient has had at least 270 days (i.e., 9 months) of follow-up after the end of the acute period, a total of 540 days (i.e., 18 months) of follow-up. The time to the occurrence of severe late GU/GI toxicity is defined as the time interval from start of protocol treatment to the date of onset of grade 3-5 GU/GI toxicity. The time analysis for recording severe late GU/GI toxicity for this protocol will be limited to 540 days from start of protocol therapy. If no such toxicity is observed before the time of the analysis, the patient will be censored at the time of the analysis. The hazard rate will be estimated by the life table approach with a time span of 18 months. The one-sided Z-test will be used to test the significance of the difference between the logarithm of the observed hazard rate and the logarithm of the hypothesized hazard rate of 0.006/month with variance equal to the reciprocal of the number of cases with late toxicity observed. Because of the lead time of 9 months for the acute period, the 18-month late toxicity will be estimated by the 9-month toxicity rate using the cumulative incidence approach [37] to the defined time to severe late GU/GI toxicity.

13.5.3 *Estimation of Secondary Endpoints Related to the Efficacy:* Cumulative incidence approach [37] will be used to estimate the failure rate for biochemical, disease-specific, local-regional and distant failures. Kaplan-Meier method [38] will be used to estimate the overall survival rate.

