13.2.1 Primary Endpoint

Late severe GU and GI toxicity is defined as grade 3-5 GU and GI toxicity occurring between 270-540 days (i.e., 9-18 months) from the start of the protocol treatment. It is graded based on CTCAE v3.0. Grade 3-5 GU or GI toxicity that originally occurred prior to 270 days from start of protocol treatment will only be considered late severe GU or GI toxicity if it persists at a severity grade of 3-5 based on CTCAE v3.0 after 270 days.

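### The 9-month rate that 13.5.2 uses for 18-month late toxicity does not return the endpoint of 13.2.1, because toxicity carried over past day 270 has no dating rule

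*Combined protocol and SAP*

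**What the plan says.** Section 13.2.1 defines late severe toxicity as "grade 3-5 GU and GI toxicity occurring between 270-540 days (i.e., 9-18 months) from the start of the protocol treatment". It adds a rule for earlier events: grade 3-5 GU or GI toxicity first seen before day 270 "will only be considered late severe GU or GI toxicity if it persists at a severity grade of 3-5" after day 270. The primary endpoint therefore has new cases and carried-over cases.

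Section 13.5.2 gives every case the same event time. Time to severe late GU/GI toxicity "is defined as the time interval from start of protocol treatment to the date of onset of grade 3-5 GU/GI toxicity". Recording stops at day 540, and the hazard for the Z-test comes from a life table spanning 18 months. The last sentence of 13.5.2 appeals to the nine-month lead time of the acute period and says that "the 18-month late toxicity will be estimated by the 9-month toxicity rate using the cumulative incidence approach", applied "to the defined time to severe late GU/GI toxicity".

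Only the sample-size section uses another origin. Section 13.3.2 works by "Assuming an exponential distribution for time from the end of the acute period", that is, from day 270.

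**The concern.** The endpoint definition and the point estimate do not fit together. The estimate is a 9-month rate, so what it contains depends on where the clock starts and how a carried-over case is dated. Section 13.5.2 starts the clock at treatment and dates cases at onset; the lead-time remark and 13.3.2 suggest a clock from day 270. Neither choice, with cases dated at onset, puts both kinds of case inside the nine months.

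Objective 2.3 and section 13.3.1 make this rate the main quantity that phase II is to deliver. On the clock from day 270, which is probably the intended one, the men left out are those whose severe injury has lasted longest. The error runs towards making the treatment look safer.

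**Working it through.** **Inputs.** Late window of days 270-540 and the persistence rule (13.2.1); event time from start of treatment to onset, and a 9-month rate (13.5.2); 47 evaluable men, and hazards of 0.006 and 0.015 per month for 10% and 23% (13.3.2). The plan gives no expected number of carried-over cases, so every split below is an assumption. Follow-up is taken as complete, and only toxicity meeting 13.2.1 is counted.

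**The plan's own figures.** Over 18 months, 1 − exp(−0.006 × 18) = 10.2% and 1 − exp(−0.015 × 18) = 23.7%. Over 9 months the same hazards give 5.3% and 12.6%. The stated rates therefore match an 18-month span. This matters for the fix below.

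**Where each kind of case falls.**

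- Clock from start of treatment, as written: carried-over cases have onset before month 9 and new cases between months 9 and 18. The 9-month rate contains only carried-over cases.
- Clock from day 270: new cases fall between months 0 and 9. Carried-over cases have a negative time. The 9-month rate contains only new cases unless carried-over cases are re-dated to day 270.

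**Estimates.** Let c be carried-over cases, n new cases and N the men followed.

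- Rate under 13.2.1: (n + c)/N.
- Clock as written, month 9: c/N.
- Clock from day 270, month 9: n/N if carried-over men stay in the denominator, or n/(N − c) if they leave the risk set.

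c/N and n/N are plainly no larger than (n + c)/N. For the third, (n + c)/N − n/(N − c) = c(N − n − c)/[N(N − c)], which is never negative. So no version exceeds the true rate.

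| New n | Carried over c | (n + c)/47 | c/47 | n/47 | n/(47 − c) |
|---|---|---|---|---|---|
| 8 | 0 | 17.0% | 0.0% | 17.0% | 17.0% |
| 5 | 3 | 17.0% | 6.4% | 10.6% | 11.4% |
| 9 | 2 | 23.4% | 4.3% | 19.1% | 20.0% |
| 6 | 5 | 23.4% | 10.6% | 12.8% | 14.3% |

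If carried-over cases are dated at day 270 on the restarted clock, the result is (n + c)/47 in every row. The 18-month rate on the clock as written gives the same.

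**The Z-test.** z = ln[(D/PT)/0.006] × √D, where D is the number of late cases and PT is person-months over the 18-month span. Men without an event contribute 18 months and new cases an assumed 13.5. Take 8 new cases and 1 carried over, so D = 9.

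- Carried-over case dated at month 3: PT = 38 × 18 + 8 × 13.5 + 3 = 795, z = 1.90.
- Same case dated at day 270: PT = 684 + 108 + 9 = 801, z = 1.88.

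Both exceed 1.645, so the dating does not change the decision in this example.

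**The case against.** Four points can be made for the plan.

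1. Section 13.5.2 refers to the date of onset of a toxicity without saying that this is the first onset. The variable is time to severe late toxicity, and an early event becomes late only by persisting past day 270. Dating it when it qualifies, on a clock from day 270, would put both kinds in the 9-month rate. This reading is available, so it would go too far to say that no reading works. But no section states it, and 13.2.1 itself treats the earlier date as when the toxicity occurred. A primary estimate should not rest on an unstated convention.

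2. The literal clock is probably not what was meant, given the lead-time remark. That is fair, but the other clock still omits carried-over cases unless they are re-dated.

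3. A reader might infer that one carried-over case can decide whether the treatment is rejected, since 8 cases give z = 1.41 and 9 give z = 1.87 (all new, at 13.5 months). The documents do not support this. That gap is the effect of any ninth event. The test uses an 18-month span from start of treatment and the number of late cases, and 13.2.1 decides which cases those are, so both kinds can enter.

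4. Carried-over men are not lost from the trial's reporting. Severe toxicity before day 270 is a secondary endpoint, and interim reports list toxicity by frequency and severity. This stands, but it does not repair the primary rate.

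**Conclusion.** The concern holds for the point estimate of the 18-month late toxicity rate, and only there. As written, that estimate contains only carried-over cases; on a clock restarted at day 270 with cases dated at onset, it contains only new ones. With complete follow-up, and counting only cases that meet 13.2.1, it can equal the true rate or fall short of it, but cannot exceed it.

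The size depends on a split that the documents do not give. With 5 new and 3 carried-over cases among 47, 17.0% is reported as 6.4%, or as 10.6% to 11.4%. With no carried-over cases, the restarted clock has no bias, while the clock as written gives zero. The Z-test is not shown to change.

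**What to change.** Replace the last sentence of 13.5.2: the late-toxicity rate is the cumulative incidence at 18 months (day 540) on the existing start-of-treatment clock, counting every case that meets 13.2.1. Alternatively, for this estimate only, start at day 270, give carried-over cases an event at day 270, and read the rate at day 540. With complete follow-up the two agree. With deaths or losses before day 270 they need not, so the plan should name one. Tabulate carried-over and new cases separately.

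Do not move the Z-test to the day-270 clock while its null stays at 0.006 per month. That null means 10.2% over 18 months but 5.3% over 9. On a 9-month clock with new cases at 4.5 months, 5 new cases among 47 (10.6%) give PT = 5 × 4.5 + 42 × 9 = 400.5 and z = 1.64, and 6 give z = 2.27. With 4 new cases and 1 dated at day 270, z = 1.66. The rejection limit would drop from 9 cases to 5 or 6.

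The cost is one or two sentences. No new patients, visits or data are needed, since adverse events are already collected at 9, 12 and 18 months. The reported rate may be less favourable.

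### The primary toxicity analysis censors every event-free man at the analysis date, so men lost or withdrawn earlier add unobserved event-free time and bias the late-toxicity hazard and rate downward

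*Combined protocol and SAP*

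**What the plan says.** Section 13.5.2 times the primary analysis by follow-up: "This analysis will be carried out when each patient has had at least 270 days" beyond the acute period, 540 days in all. Time to toxicity runs from the start of treatment, and its recording "will be limited to 540 days from start of protocol therapy". For a man without an event there is a single instruction: "If no such toxicity is observed before the time of the analysis, the patient will be censored at the time of the analysis".

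The section then names two estimators. For the test, "The hazard rate will be estimated by the life table approach with a time span of 18 months", and the log hazard is compared with log 0.006 per month, "with variance equal to the reciprocal of the number of cases with late toxicity observed". For the reported rate, "the 18-month late toxicity will be estimated by the 9-month toxicity rate using the cumulative incidence approach", with a competing-risks reference.

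No section gives a separate censoring date for withdrawal, loss to follow-up or death. Section 10.5.5 follows all men for survival but does not link death to the toxicity analysis. Section 13.2.1 adds that a toxicity starting before day 270 will "only be considered late severe GU or GI toxicity if it persists at a severity grade of 3-5" after that day.

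**The concern.** Taken as written, a man last seen at month 3 is censored at the analysis date. By inference from the 540-day limit, that means about month 18, so he contributes 15 months of event-free time in which toxicity could not have been recorded. The numerator is unchanged and the denominator is too large.

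The test asks whether late grade 3-5 GU/GI toxicity exceeds 10%. For lost or withdrawn men the error therefore lowers the estimate and makes it harder to reject a treatment that is too toxic. Because the rule is explicit, an analyst who follows it gets the lower figure, while one who uses ordinary last-contact censoring gets a different primary result from the same data.

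**Working it through.** **Inputs from the plan (13.3.2 and 13.5.2).** Null 10% (0.006/month), alternative 23% (0.015/month), one-sided 0.05, power 90%, 12 events, 47 patients, 50 with the allowance. Test: Z = √D × ln[(D/PT)/0.006], where D is events and PT is person-months.

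**The plan's own figures.**
- Events: (1.645 + 1.282)² / ln(0.015/0.006)² = 10.2, rounded up to 11 (12 stated).
- Patients: 11 / (1 − e^(−0.015×18)) = 11/0.2366 = 46.5, so 47.
- Allowance: 47/0.95 = 49.5, so 50.

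The design reproduces closely enough to use as the base.

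**Worked example.** Assume 47 men, 8 events at a mean of 13.5 months (the middle of months 9-18), and the other 39 carried to month 18.
- Rule as written: PT = 39×18 + 8×13.5 = 810; Z = 2.828 × ln(0.00988/0.006) = 1.41. Not rejected at 1.645.
- Three event-free men last seen at month 3, censored there: PT = 810 − 3×15 = 765; Z = 1.57. Not rejected.
- Four such men: PT = 750; Z = 1.63. Not rejected.
- Five such men: PT = 735; Z = 1.69. Rejected.

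Neighbouring results do not change with five such men: 7 events give 0.95 against 1.21 (neither rejects), and 9 events give 1.87 against 2.16 (both reject).

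**Same example with an actuarial single-interval life table.** Hazard = D / [18 × (N − W/2 − D/2)], where W is withdrawals.
- Five men treated as event-free to the end (W = 0): 8/(18×43) = 0.01034; Z = 1.54.
- Treated as withdrawals (W = 5): 8/(18×40.5) = 0.01097; Z = 1.71.

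**Average effect.** The loss rate is assumed. Model A has 47 men, constant toxicity hazard 0.015/month over 18 months (true rate 23.7%) and independent exponential loss. If lost men are carried forward, the expected rate is λ/(λ+μ) × [1 − e^(−18(λ+μ))]. At 5% loss, μ = −ln(0.95)/18 = 0.00285, giving 0.840 × 0.275 = 23.1%. Power and null rejection come from 100,000 simulated trials per scenario:

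| Loss by 18 months | Rate: carried / last contact | Power: carried / last contact | Null rejection: carried / last contact |
|---|---|---|---|
| 0% | 23.7% / 23.7% | 0.817 / 0.817 | 0.048 / 0.048 |
| 5% | 23.1% / 23.7% | 0.794 / 0.827 | 0.043 / 0.058 |
| 10% | 22.5% / 23.6% | 0.764 / 0.834 | 0.037 / 0.065 |
| 20% | 21.3% / 23.7% | 0.706 / 0.814 | 0.028 / 0.063 |

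The zero-loss power of about 0.82, below the stated 90%, arises because the event count varies from trial to trial. It is separate from this point.

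Model B has 50 men, a true rate of 23%, toxicity uniform over months 9-18 and drop-out uniform over months 0-18. Rejection as written against censoring at exit is 78.8% v 80.5% at 5% drop-out, 74.5% v 76.5% at 10% and 69.6% v 72.2% at 15%. The crude rate falls by 23% × drop-out × 13.5/18, which is 0.9 points at 5% and 1.7 at 10% (23% to 21.3%).

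A 9-month window with the same 10% and 23% rates gives a similar picture: 22.5% against 23.0% at 5% loss, and 20.8% against 23.0% at 20%.

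**The case against.** **The sentence is only administrative censoring.** It follows a condition that every man has 540 days of follow-up, so it can be read as covering fully followed men and leaving early leavers unaddressed. That is a fair account of the likely intent. But the condition sets when the analysis is run and cannot make a lost man observable. No other rule applies to him.

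**A life table already handles withdrawals.** An ordinary actuarial table gives them half exposure. That helps only if they are classed as withdrawals, and the stated rule does not class them so. The 1.54 and 1.71 above differ for exactly this reason.

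**The effect is small.** This largely stands. The only allowance in the plan is 5%, which also covers ineligible men, and the change of decision is a selected case with 5/47 = 10.6% lost early. In Model B most of the lost power comes from events that leave with the patients, which better censoring does not recover.

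**Stronger readings that the documents do not support.**
- A reader might infer that deaths also bias the reported rate. They do not: under cumulative incidence a man who dies of another cause stays in the denominator and can have no later event.
- A reader might infer that 13.3.2 contradicts 13.5.2, because "Considering 5% ineligible cases and lack-of-data cases" suggests such men are dropped while 13.5.2 keeps them. The sample-size text does not say how they are analysed, so this is inference.
- A reader might infer that a fatal toxicity before day 270 disappears. Its place in the primary analysis is unclear under 13.2.1, but 13.2.2 reports it as acute toxicity and the 14.2 stopping rule covers grade 3-5 GU/GI events.
- A reader might assume that men leave because of complications. Nothing in the documents shows this, and if it were so, censoring at exit would not remove the bias.

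**Conclusion.** The point holds for men lost or withdrawn before day 540. The stated rule, followed literally, gives them unobserved event-free time, lowers both the hazard and the rate, and weakens the one-sided safety test. For deaths without toxicity only the life-table hazard is diluted.

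The size rests on an assumed loss rate. It is nil with no loss. At 5% loss it is about 0.6 percentage points and 3 points of power in Model A (0.9 and 1.7 in Model B). At 10% it is about 1.1 percentage points in Model A (1.7 in Model B) and 2 to 7 points of power across the two. It grows beyond that. Carrying men to day 540 is itself inferred from the 540-day limit, because the plan does not reconcile that limit with the analysis date.

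A reader might conclude that the trial's decision is generally at risk. It is not: the conclusion changes only in borderline results such as the 8-event example. The change is still worth making because a written rule for the primary endpoint gives the wrong answer and one sentence corrects it.

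**What to change.** Replace the censoring sentence in 13.5.2 with:

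*A patient without a qualifying event is censored at the earliest of the last adverse-event assessment, withdrawal or loss to follow-up, and day 540; death without qualifying GU/GI toxicity is a competing event in the cumulative incidence estimate and ends person-time in the hazard estimate.*

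As a minor addition, state in 13.2.1 whether a grade 5 GU/GI toxicity before day 270 counts in the primary analysis.

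The cost is wording. Adverse-event assessments are already scheduled in 11.1 and Appendix I. Section 11.1 lists no withdrawal or loss date, so check that the case report forms record one. Expect a slightly higher reported toxicity rate. Rejection under the null also rises slightly above 0.05 with the plan's small-sample Z-test: about 0.058 at 5% loss in Model A, against 0.043 under the present rule.
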